## 7.4 CONSENT

An informed consent form will be provided by the investigator to be used in the patient informed consent process. As per clinical investigation regulations, written informed consent must be obtained prior to participation in the study.

The information will be given in both written and oral form. This communication will be in a language understandable to the patient and may not include any language that seems to waive any of the patient's legal rights to release the Investigator, Sponsor or the Institution from liability or negligence.

The Investigator must provide sufficient time for a prospective patient to consider whether or not to participate and must completely answer any questions raised by the patient. The investigator will explain to the patient that withdrawal from the study will be possible at any time without detriment to the participants' current or prospective medical care.

The procedure as well as topical clindamycin will be performed free of cost to the participants. Following conclusion of the study, any consequent follow-up visits and or consultations with associated medical personnel, not directly related to the study will be charged at their normal costing schedules. An example is continuing to visit the appropriate dermatologist for treatment and management of other dermatological conditions.

# 8. PARTICIPANT SAFETY AND WITHDRAWAL

## 8.1 RISK MANAGEMENT AND SAFETY

As part of standard routine care, the treating dermatologist will enquire about the patient's current medications, allergies and past medical history to ensure the procedure is appropriate. Furthermore, the participants will be given local anaesthetic to minimize pain from follicular unit extraction. Participants, as part of standard routine care, may also be given pain analgesia to manage their as well as other medications to manage the inflammation in their hidradenitis suppurativa.

## 8.2 HANDLING OF WITHDRAWALS

Participants are free to withdraw from the study at any time without providing reason(s) for withdrawal and without prejudice to further treatment. The reason(s) for withdrawal will be documented in the CRF.

Collected data from study visits will be stored at Sinclair Dermatology Clinical Trials Unit for 5 years then discarded. Samples and data will not be kept for future separate studies.

### 8.2.1 WITHDRAWAL CRITERIA

Participants may be considered withdrawn if they state an intention to withdraw, fail to return for visits, or become lost to follow-up for any other reason.

The investigator should withdraw the subject from study if he/she believes that there is insufficient response to follicular unit extraction or that continuation would be detrimental to the subject's well-being. The investigator has the right to terminate the study at any time in case of a serious adverse event (SAE) or if special circumstances arise that may disadvantage the participant, making further treatment impossible.

They may be withdrawn from the study for any of the following reasons:

- consumption of medication which may interfere with study measurements
- severe AE assessed as treatment-related by the investigator
- non-compliance with protocol
- unsatisfactory therapeutic effect
- Lost to follow-up
- Withdrawal for another reason

Participants withdrawing from the study will be encouraged at the time of withdrawal, to complete the evaluations listed for the Unscheduled visit with an explanation as to why the participant is withdrawing from the study. The aim is to record data in the same way as for participants who have completed the study.

Even if participants are not withdrawn from the study, they can choose to withdraw their permission for their anonymous data and de-identified samples to be kept for future study use.

Any adverse events (AE)s that are continuing at the time of withdrawal from the study, should, wherever possible, be followed to resolution or stabilization, whichever is earlier.

Reasonable efforts will be made to contact participants who are lost to follow-up. These must be documented in the participant's file.

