## 2. STUDY SYNOPSIS

Provide brief information

Title:	Hidradenitis suppurativa treated with follicular unit excision: A prospective controlled pilot study
Short Title:	Hidradenitis suppurativa treated with follicular unit excision: A prospective controlled study
Design:	Open-label, interventional
Study Centres:	Sinclair Dermatology, Melbourne Australia
Hospital:	
Study Question:	How effective is follicular unit excision for the treatment of mild-moderate hidradenitis suppurativa?
Study Objectives:	
Primary Objectives:	The study's primary objective is to determine change in several hidradenitis suppurativa assessment scores score throughout follow-up visits in the first 24 weeks after follicular unit excision
Secondary Objectives	
 
i) To compare the changes in Hidradenitis Suppurativa assessment scores between intervention and control groups up to 24 weeks and on the treated sites before and after follicular unit extraction
 
ii) To compare the number of disease flares between the treated and control groups for 24 weeks after treatment
 
iii) To determine if specimens contain hair follicles, sebaceous glands, apocrine glands and eccrine glands on histopathology
 

Key Inclusion Criteria:	
 
i) Patients aged <math>\geq 18</math> years with hidradenitis suppurativa
 
ii) Mild-moderate hidradenitis suppurativa defined by Hurley stage 1 up to 2A
 
iii) Minimum diagnosis of 3 months prior to baseline
 
iv) Active hidradenitis suppurativa present for <math>\geq 3</math> months from initial diagnosis
 

Key Exclusion Criteria:	
 
i) Current treatment with systemic antibiotics, retinoids, immunosuppressants or biologic agents at discretion of the investigator
 
ii) Extensive scarring
 
iii) Absence of terminal hairs in target areas
 
iv) Previous laser hair removal in target areas
 
v) Pregnant or lactating women
 

Number of Planned Participants :	24
Investigational procedure:	Follicular unit excision using 0.8 mm Ertip® punch
Data analysis	The primary objective is to evaluate the efficacy of follicular unit excision in the treatment of adults with mild to moderate hidradenitis suppurativa. The primary analysis will be conducted to assess the primary and secondary endpoints once all participants have completed the Week 24 visit.
Safety considerations:	

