#### 6.4.1.6 MANAGEMENT OF FLAREUPS

Participants may be given medications to prevent flares to stabilize the condition prior to follicular unit extraction. This may be resorcinol 15% cream and/or oral antibiotics such as doxycycline 100mg. Often, flareups may need surgical management or intralesional corticosteroids. These are given as part of standard routine care to minimize flare-ups for the hidradenitis suppurativa and alleviate symptoms for patients and is part of management guidelines.

Participants may be given a sheet to document their flareups (Appendix 3). Participants may take photos of the flareups on their phone to show to the investigator but this is optional only. Investigators will not be collecting photos taken by participants.

Participants are divided into the intervention group and control group. The control group will be managed with topical clindamycin. A staff member of Sinclair Dermatology not involved in this study will randomise participants into the intervention and controlled group using the program from [www.randomizer.org](http://www.randomizer.org) in a 1:1 stratification ratio. The treatment group will be treated with follicular unit extraction. Due to the study design (the intervention being surgical and the controlled group being a topical application), investigators and participants are unable to be blinded as to which participants will be in the treatment or control group. As there will be 24 participants in this study, numbers 1-24 will be randomly allocated to either control or treatment group using [randomizer.org](http://randomizer.org) prior to recruitment of the study. Participants will then be allocated a number in the order in which they are recruited in the study and subsequently will be placed in the group that the number has been randomised into.

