## 8.4 REPLACEMENTS

There will be no replacements if participants withdraw.

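### Section 8.2.1 directs withdrawal from the study for poor response to FUE and provides no scoring to Week 24 afterwards, so Week 24 data go missing because of the outcome

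*Protocol*

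**What the plan says.** Section 8.2.1 contains two statements on lack of effect.

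- A directive: "The investigator should withdraw the subject from study if he/she believes that there is insufficient response to follicular unit extraction". The same sentence goes on to a separate ground, the participant's well-being.
- A discretionary list, introduced by "They may be withdrawn from the study for any of the following reasons". It includes "unsatisfactory therapeutic effect" and "consumption of medication which may interfere with study measurements", and names no arm.

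On data after withdrawal, the section says: "Participants withdrawing from the study will be encouraged at the time of withdrawal, to complete the evaluations listed for the Unscheduled visit". It adds the aim of recording data as for completers. The schedule in Appendix 2 has a screening assessment and Visits 1 to 4, and no unscheduled visit. Section 8.3.5 counts as complete only those followed to Week 24. Section 8.4 states: "There will be no replacements if participants withdraw".

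FUE takes place once, at Visit 1 (Sections 6.4.2.2 and 6.5, Appendix 2). Only the intervention group receives it. For the other arm, Section 6.4.1.6 says: "The control group will be managed with topical clindamycin". Section 6.6 states that neither investigators nor participants can be blinded. Scores are taken at Weeks 0, 6, 12 and 24 (Section 6.4.1.8). The primary objective in the synopsis is change in the HS scores over the 24 weeks after FUE.

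**The concern.** Stopping a treatment for lack of effect is different from stopping measurement. With a single procedure already done, withdrawal for poor response changes nothing about FUE; its effect on the trial is that later scores are not taken. The decision is made by someone who knows the arm. It has no threshold or time point and depends on the quantity the trial is meant to estimate. Week 24 values would then be missing selectively among participants doing badly after FUE.

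Two comparisons are exposed. The before/after comparison in the FUE arm is affected whatever happens in the control arm. The between-arm comparison is affected if FUE failures leave more often than control failures, which the contrast between 'should' for FUE and 'may' for anyone makes likely. Sections 9.1 and 9.2 say the results will inform sample sizes for later studies, so a distorted effect would carry forward.

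**Working it through.** **No plan figure to reproduce.** The protocol gives no alpha, power, effect size or SD. Section 9.2 gives 12 per group, and 12 + 12 = 24 agrees with Section 9.1. Everything below is illustration. The response rates, withdrawal shares and correlations are assumptions, and no true difference between arms is assumed throughout.

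**1. HiSCR, observed data only.** Let p be the true response rate and w the share of FUE non-responders withdrawn. The observed FUE rate is p / (1 − (1 − p)w).

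- p = 0.40, w = 0.5: 0.40 / (1 − 0.60 × 0.5) = 0.40 / 0.70 = 57%. In an arm of 12 this is 4.8 responders among 8.4 completers, with 3.6 withdrawn.
- p = 0.40, w = 0.25: 0.40 / 0.85 = 47%. With w = 0.75: 0.40 / 0.55 = 73%.
- w = 0.5, p from 0.20 to 0.50: 33% to 67%.

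If no control is withdrawn, the spurious gap at p = 0.40 and w = 0.5 is 57 − 40 = 17 points. If control non-responders are withdrawn at half that share (w = 0.25), it is 57 − 47 = 10 points. If the shares are equal, the gap is zero, but both arms are overstated.

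**2. Continuous change score, observed data only.** Suppose the worst fraction q of the FUE arm at Week 12 is withdrawn, and Week 12 and Week 24 changes correlate at ρ. The shift in the completers' Week 24 mean toward improvement is ρ·φ(z)/(1 − q) SD, where z is the (1 − q) normal quantile and φ the normal density. For q = 0.2: z = 0.842, φ(z) = 0.280, and 0.280 / 0.8 = 0.350. Multiplying by ρ = 0.5 and ρ = 0.8 gives 0.18 and 0.28 SD.

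A simulation with 12 per arm, 6,000 trials per setting and a two-sided unpaired t test at 0.05 agreed with the formula. The last column gives the simulated bias if the Week 12 value is carried forward instead.

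| Withdrawn from FUE arm only | Shift toward FUE, completers (ρ 0.5 to 0.8) | False positives favouring FUE (nominal 2.5%) | Bias against FUE, last value carried forward (ρ 0.5 to 0.8) |
|---|---|---|---|
| 10% | 0.10 to 0.16 SD | 4% to 6% | 0.09 to 0.03 SD |
| 20% | 0.18 to 0.28 SD | 6% to 9% | 0.15 to 0.05 SD |
| 40% | 0.32 to 0.52 SD | 10% to 17% | 0.19 to 0.08 SD |

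**3. Equal withdrawal in both arms.** The simulated between-arm bias was within 0.01 SD, and false positives favouring FUE stayed between 2.2% and 2.8%. The FUE before/after mean among completers is still shifted by the amounts in the second column, because that comparison does not use the control arm.

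**The case against.** A reader might infer that the rule deletes treatment failures from the FUE arm alone and so biases Week 24 toward FUE as a matter of course. The protocol does not support that, for three reasons.

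- **Not one arm only.** The discretionary list allows withdrawal for lack of effect without naming an arm, so control failures can leave too. The asymmetry is between an instruction and a permission, and the between-arm bias depends on how differently the two are used.
- **Not deleted.** Scores up to withdrawal are kept, Weeks 6 and 12 are comparison points in their own right (Section 6.2), and an evaluation at withdrawal is encouraged. What is lost is scoring after withdrawal.
- **Direction not fixed.** Section 9.3 names a test but no analysis set or missing-data rule, which may stand in an SAP that is not shown. Carrying the last value forward reverses the direction. Counting withdrawn participants as HiSCR non-responders removes the responder inflation. The synopsis wording "once all participants have completed the Week 24 visit" sets the time of analysis; it does not define a completers-only population.

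Two further points are fair. The double-digit false-positive rates need heavy withdrawal: 40% is 4.8 of 12. The only attrition figure in the protocol is 20% loss to follow-up (Section 9.1), or 2.4 of 12. The interfering-medication item adds little, since it is discretionary, covers both arms, and Sections 6.4.1.6 and 8.1 allow other medication as routine care.

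These points limit the claim without removing it. The directive remains, it depends on the outcome, and an SAP cannot recover Week 24 scores that were never taken.

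**Conclusion.** The concern stands in a limited form. As written, Section 8.2.1 makes Week 24 outcomes missing because of poor response to FUE, on an unblinded judgement, with no provision for scoring afterwards. If observed Week 24 data are analysed, the FUE before/after result is too favourable, by about 0.18 to 0.28 SD with the worst 20% withdrawn. A true 40% HiSCR rate appears as 57% with half of the non-responders withdrawn. The between-arm result is biased toward FUE only to the extent that FUE failures are withdrawn more often than control failures. These sizes rest on assumed rates, shares and correlations, and the direction can reverse under other handling. That dependence on the method chosen is itself a reason to secure the data in the protocol. With 12 per arm and no replacements, a few withdrawals are enough to matter, even in a pilot.

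**What to change.** Reconcile the directive and the discretionary statement on lack of effect in Section 8.2.1. Leave the well-being ground and clinical care as they are; no view is taken here on which clinical rule is right. Then separate any such decision from outcome collection by adding:

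*Participants in both arms continue to be scored at Weeks 6, 12 and 24 whatever their response or other treatment, unless they withdraw consent to follow-up, and are analysed in the arm allocated.*

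Either define the unscheduled visit in Appendix 2 or remove the reference to it. The cost is protocol wording and a few more visits, all already in the schedule, for participants who would otherwise have left.

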### 5.3 BACKGROUND INFORMATION

HS was once considered a disease of the apocrine gland, but newer evidence firmly implicates direct follicular involvement in disease pathogenesis. Over 95% of early lesions (< 3 days old) include

hyperkeratosis, occlusion of the follicular unit and an associated perifolliculitis. These are often accompanied by dilatation of the hair follicle (HF) and subsequent stasis in both the apocrine and eccrine glands. While apocrine stasis, hyperplasia and a periglandular inflammatory infiltrate are observed in and around the apocrine glands in 33–90% of cases of HS, they are universally accompanied by extensive inflammation of the HF, eccrine gland and cystic structures, and are thought to be a secondary phenomenon. It has recently been observed that there is a thinning of the basement membrane zone around the junction between the HF and sebaceous gland in HS skin. This area of weakness may predispose to rupture of the hair follicle and spillage of its contents into the dermis and a subsequent inflammatory response. Furthermore, the identification of free keratin filaments in the dermis supports that mechanism and is consistent with follicular rupture playing a key role in disease pathogenesis.

The management of HS is currently multifactorial. Lifestyle changes e.g., smoking cessation and weight loss can reduce the frequency of HS flares. Other lifestyle modifications such as wearing loose clothing may reduce the severity of flares. Systemic therapy includes antibiotics, hormonal therapy e.g. spironolactone, retinoids and immunosuppressants. However, the disease often recurs following therapy interruption or discontinuation. The tumour necrosis factor- $\alpha$  inhibitor adalimumab is a relatively effective treatment, with 41.8-58.9% of adult patients achieving satisfactory clinical response. In chronic refractory cases, surgery, including deroofing and incision and drainage or ablative lasers may be used. Therefore, early intervention is critical to prevent progression of disease to a disfiguring recalcitrant stage.

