### 6.5 STANDARD CARE AND ADDITIONAL TO STANDARD CARE PROCEDURES

Standard Care Procedures		
Procedure	Time/Visit	Dosage/Volume
Resorcinol 15%/topical clindamycin	Week 0	Applied to affected area as needed when there is flare.

Additional To Standard Care		
Procedure	Time/Visit	Dosage/Volume
FUE	Visit 1	NA

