## 6.6 RANDOMISATION

A staff member of Sinclair Dermatology not involved in this study will randomise participants into the intervention and controlled group using the program from [www.randomizer.org](http://www.randomizer.org) in a 1:1 stratification ratio. The treatment group will be treated with follicular unit extraction. Due to the study design, investigators and participants are unable to be blinded as to which participants will be in the treatment or control group. As there will be 24 participants in this study, numbers 1-24 will be randomly allocated to either control or treatment group using [randomizer.org](http://randomizer.org) prior to recruitment of the study. Participants will then be allocated a number in the order in which they are recruited in the study and subsequently will be placed in the group that the number has been randomised into.

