## 7.3 EXCLUSION CRITERIA

Participants fulfilling any of these criteria are not eligible for inclusion in this study:

1. Current treatment with antibiotics, retinoids, immunosuppressants or biologic agents at the discretion of the investigator/research team.
2. Extensive scarring.
3. Absence of terminal hairs in target areas.
4. Previous laser hair removal in target areas.
5. Pregnant or lactating women.

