### 8.3.5 DEFINITION OF COMPLETED PARTICIPANTS

A participant will be deemed to have completed the study once the participant had follicular unit extraction or had topical clindamycin and followed up as part of standard routine care up to week 24.

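### Withdrawal from the study for medication use ends scheduled outcome collection, with no provision to continue the remaining Week 6, 12 and 24 scores or the flare diary

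*Protocol*

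**What the plan says.** Section 8.2.1 lists grounds on which participants may be withdrawn from the study. One is "consumption of medication which may interfere with study measurements". No drug, route, dose or time window is attached to it. The nearest list is the entry exclusion in section 7.3: "Current treatment with antibiotics, retinoids, immunosuppressants or biologic agents at the discretion of the investigator/research team".

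For those withdrawn, section 8.2.1 encourages them "to complete the evaluations listed for the Unscheduled visit" and adds: "The aim is to record data in the same way as for participants who have completed the study". Continuing adverse events are followed where possible. No other follow-up after withdrawal is described, and section 8.4 rules out replacement.

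Other relevant provisions:
- Section 6.6: "investigators and participants are unable to be blinded as to which participants will be in the treatment or control group".
- Section 6.4.1.8: severity is scored at Weeks 0, 6, 12 and 24.
- Section 6.7: the flare diary is reviewed at the study visits.
- Section 6.4.2.2 and Appendix 2: FUE is performed at Visit 1 only.
- Section 6.5: standard topical care is "Applied to affected area as needed when there is flare".
- Section 8.3.5: a completer had FUE or topical clindamycin and was "followed up as part of standard routine care up to week 24".

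**The concern.** The clause ends a participant's place in the study because of something that happens after randomisation and is probably linked to the outcome. Section 5.3 says "Systemic therapy includes antibiotics, hormonal therapy e.g. spironolactone, retinoids and immunosuppressants". A participant who starts one of these after Week 0 will often be doing so because the disease is active.

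The trial is open-label, so a discretionary rule of this kind can be applied differently in the two arms without anyone intending it. In the FUE arm there is also nothing to stop: the procedure is already done, and the only effect of withdrawal is that later scores and diary entries are not obtained.

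At stake are the score comparisons at Weeks 6, 12 and 24 and the comparison of flares over 24 weeks (section 6.2). The means and standard deviations that this pilot is meant to supply for future sample sizes (sections 9.1 and 9.2) are also affected. A statistical analysis plan can choose how to treat missing values, but it cannot recover IHS4, HS-PGA, pain, lesion-count or flare data that were never collected.

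**Working it through.** **Step 1: does anything restore the lost data?**
- The exit evaluation in section 8.2.1 is encouraged rather than required, and refers to an unscheduled visit. That visit appears neither in the visit descriptions (sections 6.4.2.1 to 6.4.2.5) nor in Appendix 2.
- Even if completed, it gives one assessment at the time of leaving. It cannot supply scores at later scheduled weeks, so the stated aim of recording data as for completers is not met.
- The diary is read at study visits, so review of it stops when visits stop.
- Data collected before withdrawal are kept. Only the remaining data are at risk.

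**Step 2: which medication is meant?** The as-needed topical is not expressly exempt, but it very probably is by implication: clindamycin is the control treatment, and section 8.3.5 counts follow-up under routine care as completion. The likeliest reach is the section 7.3 drug classes when started after Week 0.

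**Step 3: illustration of scale.** The plan gives no withdrawal rate for this reason, so the inputs k and d below are assumptions.

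Inputs:
- 12 per arm (section 9.2); 12 + 12 = 24, which agrees with sections 6.6 and 9.1.
- k = 1, 2 or 3 withdrawn from one arm. For scale only, the 20% in section 9.1 would be 0.20 × 12 = 2.4. That figure is overall loss to follow-up, not loss for this reason.
- d = the amount by which the withdrawn participants' unseen mean would differ from the arm mean m. From Appendix 1 d, 3 points is one nodule (1) plus one abscess (2), and 6 points is the width of the moderate band (10 − 4).

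If k of 12 average m + d, the mean of those left is m − k·d/(12 − k).

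| k | Week 24 scores lost, k/12 | Shift, d = ±3 | Shift, d = ±6 |
|---|---|---|---|
| 1 | 8.3% | 3/11 = 0.27 | 6/11 = 0.55 |
| 2 | 16.7% | 6/10 = 0.60 | 12/10 = 1.20 |
| 3 | 25.0% | 9/9 = 1.00 | 18/9 = 2.00 |

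With d positive, the observed mean falls and the arm looks better than it is. With d negative, which is possible if rescue treatment works, it rises by the same amount. If both arms lose the same k with the same d, the difference between arms is 0. With 3 lost in one arm and 1 in the other, it is 1.00 − 0.27 = 0.73 (d = 3) or 2.00 − 0.55 = 1.45 (d = 6). All of this applies only if observed scores are analysed without adjustment.

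**Step 4: flare follow-up.** One arm contributes 12 × 24 = 288 person-weeks.
- Withdrawal just after Week 6 loses 18 weeks each: 18, 36 or 54 person-weeks (6.25%, 12.5%, 18.75%).
- Withdrawal just after Week 12 loses 12 weeks each: 12, 24 or 36 person-weeks (4.2%, 8.3%, 12.5%).

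**Step 5: would changing this clause alone be enough?** No. The preceding paragraph of section 8.2.1 says the investigator should withdraw a participant whose response to the procedure is judged insufficient, and the same list includes an unsatisfactory effect of therapy. A participant who starts a systemic drug because of active disease could be removed under either of these.

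**The case against.** The clause is permissive and names no decision-maker. A reader might infer that an unblinded investigator is required to remove anyone who takes medication. The text does not say that: the investigator is named in the paragraph above, for other grounds.

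A reader might also infer that ordinary flare care triggers withdrawal. The Protocol points the other way. Concomitant medication is collected at Weeks 6, 12 and 24, section 8.1 allows medication for inflammation as routine care, and section 8.3.5 treats routine care as compatible with completion. Review of withdrawal criteria is listed only at Week 6, although later withdrawal is not barred. These points narrow the clause but do not remove it.

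The bias is not documented. The unseen scores would have been recorded after a new treatment was started and could be at or below the arm mean, giving no bias or a reversed one. The values of k and d are not in the plan. This stands in full.

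The analysis plan might use the exit score or a non-response rule, and whether post-rescue scores belong in the comparison is an estimand choice. That is true, but collecting the scores leaves every such choice open, whereas not collecting them closes some.

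Finally, the poor-response clause is the more serious one, since it is directive, outcome-driven and tied to one arm. That is correct, and it is why the fix must cover it.

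**Conclusion.** The point holds as a weakness in the design of follow-up. Section 8.2.1 lets medication use end participation in the study, and no provision continues the scheduled scores or the diary. The loss may be related to outcome and may differ by arm, because starting systemic treatment often reflects active disease and the arm is known to all.

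The documents do not support a claim that the clause biases the trial in favour of FUE, or by any given amount. Frequency, size and direction are all unknown. The illustrated shifts of 0.27 to 2.00 IHS4 points rest on assumed numbers withdrawn from one arm, assumed departures from the arm mean, and an analysis of observed scores only. They can take either sign or be zero. What is certain is narrower: each such withdrawal costs about 8% of an arm's later scores (1/12) and cannot be made good afterwards. The change is worth making because it is cheap, not because a large bias has been shown.

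**What to change.** Amend section 8.2.1 so that medication use may change a participant's care but does not end the Week 6, 12 and 24 assessments or the flare diary, unless the participant withdraws consent. Apply the same rule to the two response-based grounds (insufficient response to the procedure, unsatisfactory effect of therapy). Otherwise the same participants can still be removed and the change achieves little. Record each drug and its start date at the concomitant-medication reviews already scheduled at Weeks 6, 12 and 24. The participant's right to withdraw at any time (section 8.2) is unaffected.

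The cost is amendment wording and its ethics approval; no visit or assessment is added. The downside is that some later scores will reflect rescue treatment. The recorded dates let the analysis handle this, and the choice of method can be left to the statistical analysis plan.

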#### 6.4.1.8 HIDRADENITIS SUPPURATIVA SEVERITY ASSESSMENT

As part of standard routine care, participants will have the Hurley Stage of their HS, nodule count and abscess count documented at baseline. This is part of standard routine care to assess whether treatment is effective, and it will also allow us to calculate the hidradenitis suppurativa clinical response (HiSCR). HiSCR is defined as a  $\geq 50\%$  reduction in inflammatory lesion count (abscesses and inflammatory nodules), and no increase in abscesses or draining fistulas when compared with baseline. Participants will also have their hidradenitis suppurativa-physician's global

assessment (HS-PGA) and International Hidradenitis Suppurative Severity Score System (IHS4) score documented in follow-up visits. Pain will be assessed using the numerical scale 30 (NRS30) pain score (See Appendix 1).

These assessments will be done at week 0, week 6, week 12 and week 24.

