##### 6.4.2.2 VISIT 1 (WEEK 0)

This visit occurs no later than 28 days from Screening visit. The visit may occur on the same day as the screening visit provided i) the participant was given sufficient time to read through the patient information and consent form and ii) seek advice from their primary physician, family and/or friend and iii) have had their questions answered by the investigator adequately.

- Review of inclusion and exclusion criteria

- Review of medical history
- Review of adverse events (if any)
- Concomitant medication collection
- Vital Signs (Respiratory rate, heart rate, tympanic temperature, blood pressure)
- Physical Examination
- Weight
- Review of HS progress
- Follicular unit extraction and sample analysis (if intervention group)
- HS severity score assessments

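### Section 8.2.1 lets a severe treatment-related AE end study participation after FUE is already complete, so the exit removes no FUE exposure and can cost scheduled HS scores (low severity)

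*Protocol*

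**What the plan says.** Protocol section 8.2.1 introduces a list of exit reasons with "They may be withdrawn from the study for any of the following reasons", and one of them is "severe AE assessed as treatment-related by the investigator". The wording is permissive, and the exit is from the study. The protocol has no status in which a participant stops treatment but stays under observation.

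FUE is a single procedure. The Visit 1 list in section 6.4.2.2 contains "Follicular unit extraction and sample analysis (if intervention group", the lists for Visits 2 to 4 do not, and the FUE row in Appendix 2 is marked at Visit 1 only. Section 6.5 agrees. On HS scoring, section 6.4.1.8 says "These assessments will be done at week 0, week 6, week 12 and week 24".

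For those who leave, section 8.2.1 encourages them to "complete the evaluations listed for the Unscheduled visit" and adds "The aim is to record data in the same way as for participants who have completed the study". No such visit is described in section 6.4.2 or in Appendix 2. AEs still present at withdrawal should, where possible, "be followed to resolution or stabilization, whichever is earlier". Section 8.3.2 keeps AE reporting open to the end of Week 24, and section 8.3.3 has all AEs followed to study end and SAEs beyond that if needed. Section 8.4 rules out replacing withdrawn participants.

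**The concern.** An exit for toxicity makes sense when treatment continues, because leaving stops further exposure. Here the FUE participant has had the whole intervention before any such event can be attributed to it, and Visits 2 to 4 consist only of reviews, examinations and scoring. Leaving the study stops measurement and nothing else as far as FUE is concerned.

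The participants affected would be selected by an event that an investigator judges to be caused by treatment, and section 6.6 states that investigators are not blinded. Arms are 12 each (section 9.2), nobody is replaced, the synopsis times the primary analysis at completion of the Week 24 visit, and section 9.1 wants the results to inform later sample sizes. In a pilot of a procedure that the authors believe has not been tried in HS (section 5.3), what happens to HS scores after a severe treatment-related event is worth recording.

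**Working it through.** The protocol gives no figure for this exit, so there is nothing to reproduce. The 20% loss to follow-up in section 9.1 is not a severe-AE exit rate and is not used. The check is a count.

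**Inputs**
- Scheduled post-baseline scorings: Weeks 6, 12 and 24, so 3 per participant (section 6.4.1.8).
- FUE arm: 12 participants (section 9.2), so 12 × 3 = 36 planned post-baseline scorings.
- FUE sessions after Visit 1: 0 (section 6.4.2, Appendix 2).

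**Formula.** For one participant leaving at week t after FUE, scorings lost = number of {6, 12, 24} later than t. A participant who leaves at a scored visit is taken to have been scored there. FUE exposure avoided = 0 for every t.

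| Exit time | Scorings lost | Share of own 3 | Share of arm's 36 | Scheduled Week 24 score |
|---|---|---|---|---|
| before Week 6 | 3 | 3/3 = 100% | 3/36 = 8.3% | lost |
| Week 6 to before Week 12 | 2 | 2/3 = 67% | 2/36 = 5.6% | lost |
| Week 12 to before Week 24 | 1 | 1/3 = 33% | 1/36 = 2.8% | lost |

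One exit removes 1/12 = 8.3% of the arm's Week 24 scores and leaves 11 of 12.

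**Credit for the exit evaluation.** It happens once, is voluntary, and has no listed content. Suppose it is attended and includes the HS scores.
- Exit between scored visits: it adds one off-schedule score. The net counts become 3 − 1 = 2, 2 − 1 = 1 and 1 − 1 = 0. The zero is a count only, since an off-schedule score is not a Week 24 score.
- Exit at the Week 6 or Week 12 visit itself: that visit is scored anyway, so it adds nothing. The losses stay at 2 and 1.

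**Diary review.** Section 6.7 has the flare diary reviewed at each study visit. Exit at Week 6 leaves (24 − 6)/24 = 75% of the period without review, and exit at Week 12 leaves (24 − 12)/24 = 50%. This bears on the flare comparison over 24 weeks in section 6.2.

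**AE follow-up.** Three provisions cover most of it: continuing AEs are followed after withdrawal (8.2.1), reporting runs to Week 24 with participants told to report (8.3.2), and all AEs are followed to study end with no stated exception for those withdrawn (8.3.3). What remains exposed is detection of new AEs, because section 8.3.2 bases AE determination on examination and clinical evaluation, which study visits supply.

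**After the fix.** Scorings lost through this rule: 0 of 3 for every t.

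**The case against.** The best reply is that nothing has been shown to happen. The rule is permissive, the protocol describes FUE as minimally invasive and done under local anaesthetic, and no severe-AE rate is given. That stands, and it is why the point is of low severity. It does not remove the mismatch between the rule and a one-off procedure, since nothing tells the investigator to keep observing.

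A second reply is that data are still collected at exit, with the aim of matching completers. This stands in part. Completers are followed to Week 24 (section 8.3.5), and one early evaluation of unspecified content cannot match that. Lesion counts may also continue in routine care, but the protocol does not say that they would be used as study data.

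A third is that other criteria in section 8.2.1, on insufficient response and unsatisfactory effect, depend on the outcome itself and probably bias more. That is fair. They are a separate matter, and the change proposed here does not deal with them.

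A reader might infer more than the text supports:
- *That a severe AE obliges withdrawal.* It does not. The directive sentence, "The investigator should withdraw the subject from study if he/she believes", covers insufficient response or continuation harmful to the participant. With no FUE left to give, harm from continuing would mainly mean harm from attending visits, and that exception should stay.
- *That safety follow-up ends with the exit.* Sections 8.2.1, 8.3.2 and 8.3.3 largely preserve it.
- *That results will favour FUE.* The documents establish neither the number of exits nor the direction of any bias.

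**Conclusion.** The point holds as a low-severity flaw in the wording of section 8.2.1. For an FUE participant, the severe-AE exit avoids no FUE exposure and can cost 3, 2 or 1 of the 3 scheduled post-baseline HS scorings, depending on when it occurs. The scheduled Week 24 score goes in every case. The loss is mainly of efficacy scores and diary review.

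The figure of 3 of 3 is the worst case for one participant who leaves before Week 6 and attends no exit evaluation. It is not a forecast. The counts assume that withdrawal from the study ends scheduled visits, which follows from the wording because no text provides for HS scoring afterwards. In the control arm the topical is ongoing and used on demand (section 6.5), so stopping it can remove exposure, but that does not require observation to end.

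**What to change.** In section 8.2.1, make the severe-AE bullet a reason to stop study treatment, which in practice concerns the control topical, and not a reason to end observation. Add that HS assessments and AE review at Weeks 6, 12 and 24 continue in both arms unless the participant withdraws consent or attending visits would itself be harmful. The right to leave at any time under section 8.2 is unchanged. As an optional tidy-up for those who do leave, list the exit evaluations in Appendix 2.

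The cost is a wording change, made through the amendment process in section 14.4, with no new scheduled visits. The downside is that some participants would attend already scheduled visits that they might otherwise have left.
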